Establishing Effective Diagnostic Criteria for Lichen Sclerosus: A Diagnostic Test Accuracy Study (SHELLS)

Final V3.0
04 October 2024

Short title: Establishing Effective Diagnostic Criteria for Lichen Sclerosus

Acronym: *SHELLS*

IRAS Project ID: 332947

Study Sponsor: University of Nottingham

Sponsor reference: 23073

Funding Source: NIHR Advanced Fellowship

STUDY PERSONNEL AND CONTACT DETAILS

Sponsor: University of Nottingham
Head of Research Governance
Research and Innovation
University of Nottingham
[name]
[name]
[name]
Nottingham
[name]

Email: [contact]

Chief investigator: [name]
Associate Professor and Consultant Dermatologist
University of Nottingham
Centre of Evidence Based Dermatology
[name]
[name]
Nottingham
[name]

Email: [contact]

Co-investigators: [name]
Professor of Applied Dermatology Research
University of Nottingham
Centre of Evidence Based Dermatology
[name]
[name]
Nottingham
[name]

Email: [contact]

[name]
Professor of Clinical Trials
University of Nottingham
Nottingham Clinical Trials Unit
[name]
[name]
Nottingham
[name]

Email: [contact]

Study Statistician:

[name]
Statistician
University of Nottingham
Centre of Evidence Based Dermatology
[name]
[name]
Nottingham
[name]

Email: [contact]

Study Coordinating Centre:

SHELLS Research Assistant
University of Nottingham
Centre of Evidence Based Dermatology
[name]
[name]
Nottingham
[name]

Email: [contact]

SYNOPSIS

Title	Establishing Effective Diagnostic Criteria for Vulval Lichen Sclerosus: A diagnostic test accuracy study
Acronym	SHELLS
Short title	Diagnostic Criteria for Vulval Lichen Sclerosus
Chief Investigator	[name]
Objectives	
Primary objective: To test and validate expert-agreed diagnostic criteria (from previous electronic-Delphi consensus study) to establish the best predictors for vulval lichen sclerosus and subsequently develop a diagnostic tool.
 
Secondary objective: To develop training resources/manual to support the use of a future diagnostic tool.

Study Configuration	Multi-centre, cohort cross-sectional diagnostic test accuracy study.
Setting	Secondary care specialist outpatient clinics and community specialist hubs. Potential involvement of international sites.
Sample size estimate	
A sample size of 370 people (185 people with the outcome LS and 185 non-LS) is needed to target a confidence interval of 0.45-0.55 for the overall outcome proportion of 0.5 and to target a mean absolute error of 0.062 between observed and true outcome probabilities based on up to nine predictor variables.
 
The final recruitment figure of 407 participants includes a 10% increase for missing data

Number of participants	407 participants will be recruited to the study.
Eligibility criteria	
Inclusion criteria:
 
 • Adults (≥ 18 years of age) • Female • New presentation to a specialist clinic (secondary care or community hub) with a vulval skin complaint 
Exclusion criteria:
 
 • Inability to provide informed consent • Patients with surgical alteration of vulval skin as part of gender reaffirming surgery, or patients not born with a vulva • More than 2 weeks since initial consultation in specialist clinic

Description of interventions	
This is an observational study. There are 17 Delphi-agreed LS diagnostic criteria being tested in this study.
 
Patients will have one study visit lasting approximately 30 minutes. The study visit will include 2 clinical examinations for diagnostic assessment. At one centre (Nottingham), there will be a potential third assessment for testing of the inter-observer variability of the diagnostic criteria.
 
The reference standard diagnostic assessment will be undertaken by the patients' managing clinicians.
 
A trained blinded assessor will examine the patient to record the presence or absence of the Delphi-agreed diagnostic criteria.
 
Information will also be collected from the patient including, age, ethnicity, post code (for socioeconomic status), patient rating of the condition on the day of assessment, physician global assessment of severity, symptom duration, diagnosis of LS prior to clinic appointment, previous diagnosis of a vulval condition, treatments received, treatment duration, whether on active treatment at the time of recruitment, treatment length, and clinical assessment of 'early' or 'late' stage LS.
 
Clinical photographs will be taken in line with usual care and participants can opt out of these being used for research purposes if they wish.
 
Skin biopsy will be taken in line with usual care. Histological diagnosis will be recorded if patients have undergone a biopsy.

Duration of study	
Study duration: 24 months.
 
Participant duration: Participants will be involved in a single appointment that will last approximately 30 minutes.

Methods of analysis	
Descriptive analysis will be used to summarise the study population including age, gender, ethnicity, disease severity and stage, disease duration and treatment(s).
 
There will be a 2-stage analysis plan.
 
Stage 1: Developing a diagnostic prediction model
 
i. Refining the diagnostic prediction model: Multivariable backward logistic regression model with exit criteria.
 
ii. Quantifying the performance of the diagnostic prediction model: A calibration plot will assess how well predictions agree with the observed data. Smoothed calibration curves will be plotted using a loess smoother. All data for model development will be included for use in internal-external cross validation across centres (alongside bootstrapping). Discrimination will be measured using the C statistic.

	
iii. Clinical utility: Thresholds on the calibration plot will be based on clinical utility i.e. what defines high risk and trade-offs between benefits and harms, defined by patients and doctors.
 
Stage 2: Model validation
 
Internal validation to (i) obtain an unbiased estimate of the developed model's predictive performance, and (ii) adjust the developed model for optimisation). Bootstrapping and uniform shrinkage techniques will be used for analysis.
 
Inter-observer variability in the assessment of the diagnostic criteria will be calculated using the Kappa statistic.

--	---

ABBREVIATIONS

CI	Chief Investigator overall
CRF	Case Report Form
GCP	Good Clinical Practice
HRA	Health Research Authority
NCTU	Nottingham Clinical Trials Unit
NHS	National Health Service
NIHR	National Institute of Health and Care Research
LS	Lichen Sclerosus
PI	Principal Investigator at a local centre
PIS	Participant Information Sheet
REC	Research Ethics Committee
REDCap	Research Electronic Data Capture
R&D	Research and Development department
UoN	University of Nottingham

TABLE OF CONTENTS

STUDY PERSONNEL AND CONTACT DETAILS	2
SYNOPSIS	4
ABBREVIATIONS	7
1. STUDY BACKGROUND INFORMATION AND RATIONALE	10
2. STUDY OBJECTIVES AND PURPOSE	11
2.1 Purpose	11
2.2 Primary objective	11
2.3 Secondary objective	11
3. STUDY DESIGN	12
3.1 Study configuration	12
3.2 Setting	12
3.3 Index and reference tests	12
3.3.1 Index test	12
3.3.2 Reference standard	13
3.4 Study flow	13

1 STUDY BACKGROUND INFORMATION AND RATIONALE

1.1 Presentation of Lichen Sclerosus

Disorders affecting the female genital (vulval) area are common and frequently affect physical, psychological and psychosexual wellbeing.¹⁻⁴

In particular, lichen sclerosus (LS) is the most common inflammatory vulval skin condition.⁵ The overall prevalence of vulval LS has been reported to be up to 3% in postmenopausal women.⁶ The actual prevalence in the general population may well be higher, as up to 30% of affected women are estimated to be asymptomatic (or have minimal symptoms); LS can therefore go unrecognised.⁷⁻⁹ Symptoms of itching and discomfort can affect activities of daily living, for example, sitting, walking and going to the toilet. If not treated, LS can cause irreversible sticking together (scarring) of the vulval skin in both symptomatic and non-symptomatic patients. These changes further impact on normal daily activity and quality of life. Typical presentation includes symptoms of itch, discomfort, vulval splitting and painful sexual intercourse. Clinical features in early LS can be subtle with minimal inflammation (redness), pallor (whitening), and oedema (swelling) of tissues. As the disease progresses, characteristic bruising, splitting, and skin thinning are seen. Scarring with loss of normal anatomy occurs in established LS. Negative impact can lead to self-harm or suicidal thoughts.^{2,3,10}

LS is mainly diagnosed clinically. It has two peaks of clinical presentation in pre-pubertal girls and post-menopausal women.¹¹ In girls, it may be misdiagnosed for child abuse which is devastating for families. Scarring caused by untreated LS is irreversible and can prevent normal daily function such as passing urine, and in adults, sexual activity. LS is a major cause of vulval cancer,^{12,13} increasing the risk of cancer of the vulva in women and this can happen early in the disease process. Vulval squamous cell carcinoma cases have increased by 17% since the 1990s.¹⁴ The risk of developing vulval squamous cell carcinoma is 3-5% in those affected with LS, which is a 20-fold risk of vulval cancer compared to the general female population.¹⁵ This is thought to occur more frequently in those who have neglected, or inadequately treated LS.

1.2 Management and diagnosis of LS

In the UK, multiple specialities manage vulval skin conditions including dermatology, gynaecology, sexual health and primary care. Pathways of care are not well developed and not all UK regions have specialist vulval services. Teaching of vulval disease in undergraduate and postgraduate medicine is limited, leading to lack of awareness amongst the wider medical community. Delay in diagnosis⁴ and unsatisfactory clinical experience¹⁶ are often experienced by patients with LS. Patient involvement into this research development highlighted that misdiagnosis from non-specialists, ill-defined care pathways and social stigma/embarrassment preventing people seeking help are ongoing issues.

The use of biopsy to diagnose LS is controversial, and confirmatory biopsy is not necessary when typical clinical features are present.¹⁷ Histological findings can be varied and non-specific, even in clinically evident LS.¹⁸ This is likely due to sampling error; it is important to biopsy the correct area to give the greatest chance of typical histological features. UK guidelines state that biopsy is indicated if there are atypical features or diagnostic uncertainty; it is essential if there is suspicion of neoplastic change.¹⁷ Biopsy is not a routine procedure in primary care and should only be performed when necessary in secondary care by an experienced operator to minimise false-negative results.

First-line treatment with a super potent topical steroid, in conjunction with simple vulval hygiene measures, brings disease remission in 70% of adult females over a 3-month period.^{11,19} Therefore, early recognition and treatment is important as most patients respond well and progression of disease can be slowed or even halted.

1.3 Study rationale

Whilst LS can be treated, it is often difficult to diagnose, especially for non-specialists. There are no specific checklists to guide doctors in what they should be looking for. This means that LS often goes under-recognised and undertreated, with community diagnosis being delayed, preventing the initiation of early effective therapy.²⁰ Patients often self-diagnose thrush and obtain over the counter treatments. Misdiagnosis is also common when patients present to primary care/non-specialists. To aid early diagnosis, patients, primary care providers and health professionals not experienced in this field need a simple method of recognising vulval LS. Effective diagnosis will lead to earlier treatment and when needed, timely referral to specialist care. This will reduce complications such as scarring, anatomical changes and progression to vulval cancer.

A four-round electronic-Delphi consensus study has been undertaken by the University of Nottingham with international expert stakeholders to agree the most important clinical diagnostic criteria for LS (Establishing diagnostic criteria for vulval lichen sclerosis (SHELLS): an international electronic-Delphi consensus study).²¹ The study was approved by the University of Nottingham's Faculty of Medicine & Health Sciences Research Ethics Committee (FMHS 39-0722).

A total of five diagnostic features reached consensus as 'critical' and 12 were rated 'important but not critical'.

The aim of this diagnostic test accuracy study (SHELLS) is to test the Delphi criteria agreed as 'critical', and/or 'important but not critical', in the clinical setting, and subsequently develop a diagnostic tool which will support the diagnosis of LS. The diagnostic tool will be available for use by a range of health professionals (not only skin specialists) to diagnose LS as well as to help patients self-diagnose in the community.

2. STUDY OBJECTIVES AND PURPOSE

2.1 Purpose:

To develop and validate a diagnostic criteria model for vulval LS which can be used by health professionals and patients.

2.2 Primary objective

To test and validate expert-agreed diagnostic criteria (from previous electronic-Delphi consensus study) to establish the best predictors for vulval LS and subsequently develop a diagnostic tool.

2.3 Secondary objective

To develop training resources/manual to support the use of a future diagnostic tool.

3. STUDY DESIGN

3.1 Study configuration

Multi-centre, cohort cross-sectional diagnostic test accuracy study.

3.2 Setting

Research centres will comprise of UK specialist outpatient clinics in secondary and tertiary care as well as community specialist hubs. This setting is a feasible environment in which the reference standard (dermatologist's diagnosis, see below) can be obtained and the sample size recruited within the time and resources available. We anticipate that 50-60% of new patients referred to the vulval clinic will have LS.

There is potential for including international centres in this study, although it is anticipated that the majority will be in the UK.

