7 ANALYSES

7.1 Methods

[name] will undertake the analysis of the data under the supervision of [name] (Study Statistician).

Demographic data and participant characteristics will be analysed descriptively.

Stage 1

Developing a diagnostic prediction model:

i. Determining a predictive model of diagnostic criteria for vulval LS: All criteria identified will be included in a backward multivariable logistic regression model²² with exit criteria $p=0.157$.²³

ii. Quantifying the performance of the diagnostic prediction model: Explained variation will be measured by Cox-Snell R-squared. A calibration plot will assess how well predictions agree

with the observed data. Smoothed calibration curves will be plotted using a loess smoother.^{24,25} All data for model development will be included for use in internal-external cross validation across centres (alongside bootstrapping). Discrimination will be measured using the C statistic.²⁶ The model will be fitted to this dataset.

iii. Clinical utility: Thresholds on the calibration plot will be based on clinical utility i.e. what defines high risk and trade-offs between benefits and harm, defined by patients and doctors.

Stage 2

Model validation

Internal validation is essential to (i) obtain an unbiased estimate of the developed model's predictive performance, and (ii) adjust (shrink) the developed model for optimisation (if necessary). Bootstrapping and uniform shrinkage techniques will be used for analysis.

Missing data: Missing data is not anticipated as the diagnostic features will be assessed by clinical examination. There will be a 'yes' or 'no' answer recorded in the CRF for each criterion in each patient. Only if a participant declines to continue the examination or declines to be examined by the blinded assessor do we anticipate missing index-reference test data pairs. However, the sample size is increased by 10% to account for a maximum of 10% missing data. This will be monitored and if less than 10% data are missing, recruitment target will be reduced accordingly.

c. Inter-observer variability

The inter-observer reliability for assessing the individual diagnostic criteria on 20 cases and 20 non-cases from one of the sites will be calculated using the Kappa statistic. A value of Kappa >60% will be considered acceptable as 'good' agreement between observers.²⁷ At the site where these data are collected (Nottingham, lead site), there will be two independent assessors.

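### The model's probabilities and high-risk thresholds rest only on specialist-clinic referrals, and will be too high for community users if LS is less common there

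*Protocol*

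**What the plan says.** **Where the data come from.** Protocol section 3.2: "Research centres will comprise of UK specialist outpatient clinics in secondary and tertiary care as well as community specialist hubs". Feasibility is the stated reason: the specialist reference diagnosis can be obtained and the sample recruited there. The same section adds: "We anticipate that 50-60% of new patients referred to the vulval clinic will have LS". Section 7.2 sizes the study on an outcome proportion of 0.5.

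**Who the tool is for.** Section 1.3: "The diagnostic tool will be available for use by a range of health professionals (not only skin specialists"), "as well as to help patients self-diagnose in the community". Section 2.1 gives the purpose: "To develop and validate a diagnostic criteria model for vulval LS which can be used by health professionals and patients". Section 10 plans dissemination to GPs, patient social media groups and beauty therapists. Section 11 foresees rewording the final criteria for the public.

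**How cut-offs are set and checked.** Section 7.1, Stage 1 (iii): "Thresholds on the calibration plot will be based on clinical utility i.e. what defines high risk". Validation consists of bootstrapping, uniform shrinkage and internal-external cross-validation across the study's own centres. The protocol mentions no recalibration to another setting, no validation in primary care, and no limit on where the probabilities apply.

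**Prevalence outside the clinic.** The only figure is in section 1.1: "The overall prevalence of vulval LS has been reported to be up to 3% in postmenopausal women".

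**The concern.** A fitted logistic model reproduces the outcome frequency of the sample it was built on. Good calibration in this study will therefore mean good calibration among women referred to specialist vulval services, about half or more of whom have LS. A threshold placed on that plot has the same limit.

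The intended users include women and clinicians upstream of referral. Referral to a vulval clinic selects for suspected vulval disease, so it is reasonable, though an inference, to expect LS to be less common upstream. Nothing planned would reveal or correct the resulting shift:

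- Bootstrapping and uniform shrinkage deal with overfitting, not with a change in prevalence.
- Every centre held out in the internal-external validation is a specialist setting, and the community hubs are specialist hubs too.

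What is at stake is how the result is read. A probability or cut-off reported as well calibrated could be carried into a population that it does not describe.

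**Working it through.** **Inputs from the protocol.** Development prevalence d = 50-60% (3.2); outcome proportion 0.5, n = 370 evaluable and 407 recruited (7.2); up to 3% in postmenopausal women generally (1.1).

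**Inputs assumed.** Prevalence t among community users: 40%, 30%, 20% and 10%. The protocol gives no value. Sensitivity 0.90 and specificity 0.80 at the chosen cut-off are for illustration only, because no cut-off is fixed yet.

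**Step 1. The plan's own figure.** With n = 370 and a proportion of 0.5, the half-width is 1.96 × √(0.25/370) = 0.0509, giving 0.449-0.551. This rounds to the stated 0.45-0.55. Also, 370 × 1.10 = 407. For the present point this shows only that the design is built on a prevalence of about one half.

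**Step 2. Moving a clinic prediction to another prevalence.** If the feature distributions within LS and within non-LS are unchanged, only the prior odds move:

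odds at t = clinic odds × [t/(1−t)] / [d/(1−d)]

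A clinic prediction of 80% has odds of 4. At t = 20%:

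- d = 50%: 4 × 0.25/1 = 1, a probability of 50%.
- d = 60%: 4 × 0.25/1.5 = 0.667, a probability of 40%.

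| Prevalence t in use | 80% becomes (d = 60% to d = 50%) | Overstatement, points |
|---|---|---|
| 40% (assumed) | 64-73% | 7-16 |
| 30% (assumed) | 53-63% | 17-27 |
| 20% (assumed) | 40-50% | 30-40 |
| 10% (assumed) | 23-31% | 49-57 |
| 3% (extreme lower bound) | 8-11% | 69-72 |

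A clinic 80% falls below even odds once t/(1−t) is less than [d/(1−d)]/4. That is t below 20% for d = 50% (odds 1/4 = 0.25), and below about 27% for d = 60% (odds 1.5/4 = 0.375).

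**Step 3. Predictive values at a fixed cut-off.** PPV = 0.9t / [0.9t + 0.2(1−t)].

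| Prevalence | PPV |
|---|---|
| 60% | 87% |
| 50% | 82% |
| 40% | 75% |
| 30% | 66% |
| 20% | 53% |
| 10% | 33% |
| 3% | 12% |

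PPV equals 50% where 0.9t = 0.2(1−t), so t = 0.2/1.1, about 18%. Negative predictive value (NPV) moves the other way: 84-89% at 60-50% prevalence, 97% at 20% and 99% at 10%.

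**The case against.** **The size is unknown.** This stands. A reader might infer that the tool will greatly overstate LS in the community, or that most women it flags there would not have LS. The documents support neither. They give no prevalence among women presenting to primary care or checking themselves. At 40% the error at a predicted 80% is only 7-16 points. On the illustrative sensitivity and specificity, most flagged women have LS at any prevalence above about 18%. The 3% figure describes postmenopausal women in general, not women with a vulval complaint, so it is not a working estimate for users.

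**The prior-odds adjustment rests on a doubtful assumption.** This also stands. Section 1.3 describes self-diagnosed thrush and misdiagnosis by non-specialists, which suggests a different non-LS group upstream. Section 6.2 requires assessors trained in vulval examination, which patients are not. Discrimination may therefore change too, in a direction these data cannot show. The adjusted figures illustrate sensitivity to prevalence; they are not a corrected community model.

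**The study's main aim is largely untouched.** This stands in part. A reader might infer that the study cannot serve its purpose. Under the assumption in Step 2, a change in prevalence moves the intercept and leaves the predictors' odds ratios and discrimination alone. The primary objective (2.2) is to find the best predictors and then develop a tool, section 2.3 calls the tool a future one, and section 7.1 calls the validation internal. But no later validation step is described before the dissemination in section 10.

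**Cross-validation across varied centres can show differences in calibration.** True, since secondary, tertiary and hub settings are included. It still cannot represent primary care or self-assessment.

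**This belongs in the statistical analysis plan.** That may be so for the form of the tables; the plan is not shown. The purpose, setting, validation method and source of the thresholds are all fixed in the protocol, and the gap comes from their combination.

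**Conclusion.** The concern holds in conditional form. The calibrated probabilities and thresholds will describe women referred to specialist vulval services. If LS is less common among the non-specialist and self-diagnosis users named in 1.3 and 2.1, the probabilities will be too high and PPV lower, and the planned validation cannot correct this. At a clinic prediction of 80%, the overstatement is modest near 40% prevalence and at least 30 points at 20% or below.

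These sizes rest on the anticipated 50-60% clinic prevalence, on assumed prevalences in use, and on unchanged feature distributions within LS and non-LS. The recruitment setting is not a fault: it is a reasoned choice for obtaining the reference diagnosis. What needs to change is the reach of the claim.

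**What to change.** Keep recruitment and sample size as they are.

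1. In sections 1.3, 2.1 and 7.1, state that the calibrated probabilities and thresholds apply to women referred to specialist vulval clinics, and that community or self-diagnosis use is provisional until validated in that setting.
2. In section 7.1, plan to report sensitivity and specificity at the chosen threshold, with PPV, NPV and prior-odds-adjusted probabilities over a stated range of assumed prevalences. The adjustment adds ln[t/(1−t)] − ln[d/(1−d)] to the intercept, with d now the observed study prevalence. Label it a sensitivity analysis that assumes unchanged feature distributions within LS and non-LS, not a corrected community model.

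The cost is some protocol wording and a little more analysis, with no extra participants or visits. The downside is a narrower headline claim.
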